PROTOCOL and SAP

The Role of Human Fibrinogen Concentrate (RiaSTAP) in Decreasing Blood Loss and the Need for Component Blood Therapy in Infants Undergoing Cardiopulmonary Bypass

National Clinical Trial (NCT) Identification Number: NCT02822599

December 7, 2017

Purpose of Study

The goal of the study is to determine whether the use of Human Fibrinogen Concentrate (RiaSTAP) will decrease blood loss and the need for component blood therapy in neonates and infants undergoing cardiopulmonary bypass. RiaSTAP will be administered after termination of Cardiopulmonary Bypass (CPB) at a dose of 70 mg/kg, in a prospective, randomized, controlled study. We hypothesize that the administration of RiaSTAP in this manner will reduce peri-operative bleeding and transfusion requirements.

Background

Severe postoperative bleeding is a serious complication after cardiac surgery and results in increased morbidity and mortality¹². The bleeding is often multifactorial and influenced by both surgical factors and impaired hemostasis. The impaired hemostasis after cardiac surgery may be caused by enhanced fibrinolysis, platelet (PLT) dysfunction and coagulopathy secondary to the exposure of blood to artificial surfaces, and the surgical trauma³.

In children less than 12 months old with congenital heart disease, bleeding after cardiac surgery is further complicated as the fibrinogen of these patients is qualitatively dysfunctional⁴. Moreover, the coagulation systems of neonates and children undergoing CPB are profoundly affected by hemodilution⁵ and by consumption⁶. As a result, neonates and young infants undergoing complex cardiac repairs often receive multiple units of blood products, both in the operating room (OR) and intensive care unit (ICU).

Preoperative fibrinogen concentration is an independent predictor of post-operative bleeding volume. Fibrinogen concentration, even when within the normal range, is a limiting factor for post-operative hemorrhage⁷. The prophylactic infusion of fibrinogen concentrate has been shown to reduce bleeding after coronary artery bypass graft (CABG) surgery without evidence of hypercoagulability⁸. Moreover, ROTEM FIBTEM test guided fibrinogen concentrate administration was associated with reduced transfusion requirements and 24 hour postoperative bleeding in patients undergoing aortic valve operations and ascending aortic reconstructions⁹.

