Our institution has been using RiaSTAP on this high-risk patient population since April 2013. In a separate, retrospective analysis our group has compared a group of 50 patients who received RiaSTAP with 50 age, diagnosis and procedure matched patients prior to April 2013. Our analysis demonstrates that there is a statistically significant reduction in the need for FFP and cryoprecipitate, without an increase in thromboembolic events, when RiaSTAP is used at a dose of 70 mg/kg.¹⁵

Criteria For Subject Selection

Number of subjects: 30

Gender of subjects: There are no gender-based enrollment restrictions for this study. Gender distribution should reflect the gender distribution of the patient population and the gender distribution of Congenital Heart Disease (CHD) in general which is slightly skewed towards male patients in a 60:40 ratio of males to females.

Age of Subjects: Age will range from full term (at least 37 weeks gestational age) newborns to 12 months old, inclusive.

Racial and Ethnic Origin: There are no racial and ethnic restrictions for this study.

Inclusion Criteria: All neonatal and infant cardiac patients presenting for open-heart surgery at Nicklaus Children's Hospital will be eligible for enrollment in the study.

Exclusion criteria: Patients who fall outside of the age range for the study will be excluded. Patients known to have had an anaphylactic or severe reaction to the drug or its components will not be enrolled. At the time of the rewarming ROTEM, any patient with a FIBTEM MCF > 15 mm, will be excluded.

Vulnerable subjects: Patients in the study population are neonatal and infant cardiac surgical patients and are considered vulnerable subjects.

Methods and Procedures

Randomization:

We plan to enroll 30 neonates and infants scheduled for elective cardiac surgery. Patients will be randomized to one of two groups with 15 patients in each group; Group 1 will receive an infusion of RiaSTAP, right after the termination of CPB at a dose of 70 mg/kg and

Group 2 will receive a placebo of Normal Saline 0.9% (NS) during the same time period. The volume of NS will be calculated to be the same volume that would be used IF the patient were receiving RiaSTAP. This will be the only difference between the groups.

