Both Groups will receive the normal standard of care both before and especially after this event. This will be the only event that is different for the two groups. To avoid selection bias, the Pharmacy will perform the randomization using Research Randomizer. Briefly, for each patient, a randomly generated integer between 1-30 will be produced. If the number is even, the patient will be assigned to Group 1. If the number is odd, the patient will be assigned to Group 2. The randomization process and schedule will be provided by the Principal Investigator's office, but the actual patient assignment will be done by Pharmacy.

All operating room and ICU personnel will be blinded to the patient's Group assignment. The only persons who will have access to the identity of the Group assignment from the time of randomization until 24 hours after surgery will be members of the Pharmacy staff. NONE of these individuals will be involved in patient care. The DSMB will be unblinded AFTER the study treatment period concludes (24 hours after surgery).

Endpoints:

Primary efficacy endpoints will be estimated as follows:

- postoperative bleeding (EBL) during the first 24 hours (hr) after surgery (cc/kg),
- the identity and total volume of transfused blood products (cc/kg) given in the peri-operative period, separated out into its components,
- hemoglobin concentration 2 hr. and 24 hr. after surgery and
- effects of fibrinogen infusion on global hemostasis 2 hr. and 24 hr. after surgery (PT, PTT, INR, fibrinogen level, platelet count and ROTEM analysis).

Post-operative period begins after the patient leaves the operating room. The need for Factor VII use and dose will also be included as a primary end point. Factor VII is typically used only if there is profuse bleeding not amenable to component transfusion therapy.

Secondary end points will include:

- the number of post-op hours requiring ventilator support,
- Length of Stay (LOSH) in the hospital,
- Length of Stay (LOS ICU) in the Cardiac Intensive Care Unit (CICU) and
- the need for re-exploration for bleeding within the first 12 hours.

The primary safety endpoints that will be monitored are the presence of a clinical adverse events. Clinical adverse events (AEs) are defined as any clinical signs of central or peripheral thromboembolism, respiratory or circulatory failure, or allergic reactions during hospital stay. It will also include infection with a blood-borne pathogen.

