Patients under 10 kg in body weight will have the CPB pump primed with one unit of Packed Red Blood Cells (PRBC) and 200 cc Fresh Frozen Plasma (FFP). In patients over 10 kg a pure crystalloid prime will be used. Target hemoglobin (Hg) while on CPB will be 9 gm/dL, but the transfusion trigger for additional units of PRBC will be 7 gm/dL.

Drug protocol:

The following laboratory studies will be obtained prior to surgery: Complete Blood Count (CBC), Prothrombin time (PT), International Normalized Ratio (INR), Partial Thromboplastin time (PTT), Platelet count, and a Fibrinogen level; an electrolyte profile will also be done. An Activated Clotting Time (ACT) and a Thromboelastometry analysis [REDACTED], a device that assesses the viscoelasticity of whole blood and other parameters, will be done after an A-line is placed (Figure 1).

A blood products transfusion algorithm was developed based on four previous studies published in the literature, modified for pediatrics¹⁶¹⁷¹⁸¹⁹ (Figure 2). Blood is measured in the cell saver reservoir and the suction canister every fifteen minutes while in the OR. Clinically significant bleeding, requiring treatment, will be defined as a rate in excess of 10 cc/kg/hr calculated every 15 minutes while in the OR. Calculations will be done every 60 minutes in the CICU.

After rewarming, but prior to the termination of CPB a ROTEM analysis will be done. Platelets or FFP will be administered at this time, while still on CPB, if the ROTEM results indicate a deficiency of either component. Then immediately after the termination of CPB, RiaSTAP or NS will be administered depending on the group assignment. Then, as per routine care, a ROTEM analysis and fibrinogen level will be assessed and the transfusion algorithm will be continued. *If the ROTEM indicates a fibrinogen deficiency, cryoprecipitate will be given.* Thereafter, as per routine care, a ROTEM analysis will be done at least every 30 minutes while in the OR or sooner at the discretion of the OR team. Once the patient leaves the OR a ROTEM will be done at least every 60 minutes for the first six hours or until clinically significant bleeding has stopped, whichever comes first; ROTEMs can be done more frequently at the discretion of the ICU staff caring for the patient. The blood products transfused after separation from CPB will be based on the protocol below (Figure 3). Dosing amounts of the required component therapy will be based on the formula below:

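### Transfused volume per kilogram depends on infant size, yet arms are compared without any baseline covariate: this costs power and leaves chance imbalance uncorrected, but does not bias the trial

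*Combined protocol and SAP*

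**What the plan says.** **Who is enrolled.** Criteria For Subject Selection sets the age range: "Age will range from full term (at least 37 weeks gestational age) newborns to 12 months old, inclusive". The inclusion criterion is broad: "All neonatal and infant cardiac patients presenting for open-heart surgery". The Randomization text adds a qualifier: "We plan to enroll 30 neonates and infants scheduled for elective cardiac surgery".

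**Allocation.** The Randomization text plans equal arms: "Patients will be randomized to one of two groups with 15 patients in each group". Pharmacy draws one random integer per patient, and "If the number is even, the patient will be assigned to Group 1"; an odd number gives Group 2. No stratum, block or minimisation factor is named.

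**Analysis.** Statistical Analyses plans Student's t-test, Fisher's exact test, and repeated-measures ANOVA for outcomes taken at several times. No baseline covariate enters any of them.

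**Size-dependent exposure.** Under Cardiopulmonary Bypass (CPB) Management, infants below 10 kg get a prime of one red cell unit plus 200 cc of plasma. Above that weight, "In patients over 10 kg a pure crystalloid prime will be used". Footnote 12 to the Schedule of Events includes the prime in the record of total transfused products. Endpoints makes transfused volume in cc/kg, by component, a primary efficacy endpoint.

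**The concern.** A fixed volume divided by body weight gives a per-kilogram figure that falls as weight rises. Part of one primary outcome is therefore set by the infant's size before study drug is given. The depth of hypothermia also varies with the repair.

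With no covariate in the analysis, the spread between small and large infants stays in the error term. If one arm of about 15 happens to hold more small infants, the unadjusted difference carries that imbalance and nothing in the plan takes it out. At stake are power in an already small trial and the credibility of the one comparison it will produce.

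**Working it through.** **The plan's own figure.** The 30 subjects (15 per arm) cannot be reproduced, because no power, effect size or SD is given. For orientation, with two-sided alpha 0.05 (sidedness assumed) and 80% power, the detectable difference is (1.960 + 0.842) × √(2/15) = 1.02 SD by the normal formula, or 1.06 SD by the t-test.

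**1. Size dependence that follows from the documents.** Plasma in the prime, per kilogram = 200 / weight:
- 3 kg: 200/3 = 67 cc/kg
- 5 kg: 200/5 = 40 cc/kg
- 9 kg: 200/9 = 22 cc/kg
- over 10 kg: 0

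One plasma dose in the transfusion protocol is 20 cc/kg, so these differences are large on the trial's own scale.

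**2. Assumptions the documents do not supply.** 12 of 30 infants are neonates. Neonates differ from older infants by 0.5, 1.0 or 1.5 within-group SD. The true drug effect is 1 SD.

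**3. Chance imbalance.** With arms fixed at 15:15 and K neonates, the number in one arm is hypergeometric (30, K, 15). The probability that the arms differ by 4 or more is 21.5% for K = 8, 24.5% for 10, 26.4% for 12 and 27.2% for 14. Odd K is not comparable, since a difference of exactly 4 is then impossible.

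**4. What one split does.** With K = 12 and a 1 SD age shift:
- 8:4 moves the mean difference by (4/15) × 1 = 0.27 SD, and 9:3 by (6/15) × 1 = 0.40 SD. The standard error at 15 per arm is √(2/15) = 0.365 SD.
- With no drug effect, the unadjusted false-positive rate given the split is 7.3% at 8:4 and 13.7% at 9:3. With adjustment it is 5% in both.
- With a true 1 SD reduction, unadjusted power is 67% at 6:6, 40% at 8:4 with the excess in the drug arm, and 88% with the excess in control. Adjusted power at 8:4 is 72% either way.
- For the prime alone, with assumed mean weights of 3.2 and 7 kg, 8:4 gives a plasma gap of (4/15) × (200/3.2 − 200/7) = (4/15) × 33.9 = 9 cc/kg.

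**5. Averaged over all allocations** (100,000 simulated trials per setting, independent even/odd draws unless stratified, covariate = neonate indicator). Type I error as planned is 5.0%. Power for a true 1 SD effect:

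| Age shift | As planned | Stratified, unadjusted | Adjusted only | Both |
|---|---|---|---|---|
| 0.5 SD | 71% | 73% | 72% | 75% |
| 1.0 SD | 64% | 67% | 72% | 75% |
| 1.5 SD | 55% | 57% | 72% | 75% |

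Stratifying without adjusting makes the t-test conservative (type I error about 3% at a 1 SD shift). If arms are held at exactly 15:15 without strata, the 1 SD row reads 66% unadjusted and 73% adjusted. With no age effect at all, adjustment takes power from 74% to 72%.

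**The case against.** **Randomisation already covers chance imbalance.** A reader might infer that an excess of neonates in one arm would bias the trial. The documents do not support that. Allocation is random, overall type I error is 5%, and the p-value allows for such splits. The shifts in step 4 are conditional on the split that occurs. This objection stands; what remains is lost precision and an uncorrected split.

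**The matched historical comparison is no precedent.** The Background cites "50 patients who received RiaSTAP with 50 age, diagnosis and procedure matched patients", and one might conclude that the trial must stratify on the same factors. That study matched because it was retrospective and had no randomisation. It shows only that the sponsor thought the factors worth balancing.

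**The protocol does not set neonates apart from older infants.** The Background says that "neonates and young infants undergoing complex cardiac repairs often receive multiple units of blood products". This names neonates and young infants together, and the qualifier is the complexity of the repair. It also describes dysfunctional fibrinogen across the whole first year. No neonate cut-off or neonate-versus-infant difference in bleeding is given. The driver the documents do contain is weight, and it bears on transfused volume, not directly on chest tube drainage. Since the prime and each component are recorded separately, the prime can also be identified. All of this stands, and it is why the covariate may be weight as well as age.

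**Eligibility may be narrower than it looks.** The Randomization text says elective surgery while the inclusion criterion does not, and a high FIBTEM MCF at rewarming excludes a patient. The first two passages must be reconciled. Neither limit narrows the age or weight range.

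**Conclusion.** The point holds as a loss of precision that is cheap to recover. It is not an error or contradiction in the plan. The dependence of transfused volume in cc/kg on size follows from the prime rule by arithmetic. The power figures do not: they rest on an assumed 12 of 30 neonates, an assumed age shift and an assumed 1 SD drug effect. On those assumptions, adjustment alone is worth about 8 points of power at a 1 SD age shift (64% to 72%), about 1 point at 0.5 SD and about 17 at 1.5 SD. Stratified allocation adds about 3 points on top.

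A reader might take the missing strata to be the main fault. The figures say otherwise: stratifying while keeping the unadjusted t-test moves power only from 64% to 67%. The gain lies mainly in the analysis.

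**What to change.** In Statistical Analyses, replace the unadjusted t-test for 24-hour bleeding and for transfused volume with a linear model (ANCOVA) of treatment group plus one baseline covariate. Name age or body weight before unblinding; the Schedule of Events already collects body weight and demographic data before surgery. Report the adjusted difference with its confidence interval. Eligibility and clinical care are untouched. The cost is one degree of freedom, and about 1 to 2 points of power if the covariate proves not prognostic.

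Optionally, Pharmacy may hold two concealed lists by age group, with varying and undisclosed block sizes. This adds about 3 points of power when combined with the adjusted model. It may leave a small departure from 15:15, which independent even/odd draws do not secure either: they give exactly 15:15 with probability C(30,15)/2³⁰ = 14.4%. The other downside is that some later assignments become predictable, because Methods to Minimize Bias accepts that ROTEM values may reveal the study drug.

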PRBC: Volume required = Blood volume (V) x desired Hct increase / Hct of red cell unit (70%)

FFP: 20 cc/kg

Plateletpheresis: 20 cc/kg

Cryoprecipitate: 10 cc/kg

The ROTEM analysis algorithm is below (Figure 4).

Four main scenarios based on clinical observation and TEM results were possible:

1. Insignificant bleeding—normal TEM \Rightarrow no transfusions
2. Insignificant bleeding—abnormal TEM \Rightarrow no transfusions
3. Significant bleeding—normal TEM \Rightarrow surgical reevaluation
4. Significant bleeding—abnormal TEM \Rightarrow transfusion of blood products as indicated by:
 - a. fib-TEM MCF < 7 mm \Rightarrow cryoprecipitate
 - b. hep-TEM MCF < 50 mm \Rightarrow platelets,
 - c. hep-TEM CT > 240 seconds \Rightarrow FFP,
 - d. hep-TEM CFT > 110 seconds \Rightarrow cryoprecipitate and /or platelets depending on MCF

If clinically indicated (continuing bleeding) or to verify the treatment effect and control heparin reversal, a second set of in-TEM, hep-TEM, and fib-TEM analyses will also be performed during wound closure. ACT will be tested in all patients to control for heparin reversal. If patients have both a pathological ACT and TEM, protamine will be administered.

Postoperative bleeding in the ICU will be defined as the total amount of chest tube drainage after closure of the sternum and during the first 24 postoperative hours. If the sternum is not closed, it will be defined as the total chest tube drainage during the first 24 postoperative hours. An intensive care nurse blinded to group assignment will record the bleeding every hour. The amount of transfused red blood cells (RBC), FFP, cryoprecipitate and platelets during the hospital stay will be recorded in cc/kg. The transfusion triggers will be as described above. The CICU physicians and nurses will not be informed of the preoperative fibrinogen concentration or group assignment.

Patient Assessment:

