To avoid selection bias, patients will be randomized to their treatment assignment group by the research pharmacists using the Research Randomizer. The randomization procedures are detailed in the Methods and Procedures section of this protocol. All operating room and ICU personnel will be blinded to the patient's Group assignment. An intensive care nurse blinded to group assignment will record postoperative bleeding every hour. Since the study is blinded and the practitioners caring for the patient will not know if the subject received the study drug or placebo, for the study treatment period (ending 24 hours after surgery), the Cardiac Intensive Care Unit staff will monitor the incidence of adverse thromboembolic events and intervene with routine care, if necessary. In order to maintain patient safety, the ROTEM analyses must be interpreted by the anesthesiologist caring for the patient in order to guide transfusion therapy. This is the standard of care and an integral part of the protocol. The hospital staff anesthesiologists are also investigators in the study including the Principal Investigator. As part of routine care, if the ROTEM results indicate a deficiency of platelets or FFP, either component will be administered while still in the OR. In addition, if the ROTEM indicates a fibrinogen deficiency after termination of CPB, cryoprecipitate will be given. After review of the ROTEM values, the identity of the study drug may be discernable. In order to avoid the ascertainment bias from this knowledge, study data will be analyzed by a biostatistician independent of the investigator prior to any presentation or publication of study results. The biostatistician will be blinded to the study treatment assignment.

Statistical Analyses

All quantitative measures will be analyzed using descriptive statistics [mean +/- standard deviation (SD), etc.]. Treatment and placebo group comparisons will be made with the Student's t-test (continuous variables) or Fisher's exact test (categorical variables). A p-value of ≤ 0.05 will be considered statistically significant. For group comparisons of variables that will be analyzed at more than onetime point, Analysis of Variance (ANOVA) for repeated measurements will be used followed by Student's t-test if the ANOVA (group or interaction between group and time) indicated a statistically significant difference ($p \leq 0.05$).

Data Storage and Confidentiality

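### Rewarming FIBTEM decides entry and is linked to a primary endpoint, yet the planned analysis does not adjust for it

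*Combined protocol and SAP*

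**What the plan says.** - **Entry.** Criteria For Subject Selection, Exclusion criteria: "At the time of the rewarming ROTEM, any patient with a FIBTEM MCF > 15 mm, will be excluded". There is no lower limit.
- **Assigned treatments.** Randomization: RiaSTAP right after bypass in Group 1, while "Group 2 will receive a placebo of Normal Saline 0.9% (NS) during the same time period". Care is otherwise the same in both groups. Assignment is by an odd or even random integer, without strata.
- **Cryoprecipitate triggers.** Drug protocol, the four scenarios: with significant bleeding and an abnormal TEM, cryoprecipitate follows "fib-TEM MCF < 7 mm". A second route is "hep-TEM CFT > 110 seconds", leading to cryoprecipitate, platelets or both depending on MCF. Under the heading "Insignificant bleeding—abnormal TEM" nothing is transfused. Significant bleeding is a rate above 10 cc/kg/hr.
- **A differently worded instruction.** Earlier in Drug protocol, about the ROTEM after study drug: "If the ROTEM indicates a fibrinogen deficiency, cryoprecipitate will be given". No bleeding condition is attached.
- **Endpoints.** Bleeding over 24 hours and the volume of each transfused component are both listed as primary efficacy endpoints.
- **Analysis.** Statistical Analyses: "Treatment and placebo group comparisons will be made with the Student's t-test (continuous variables) or Fisher's exact test (categorical variables"), with repeated-measures ANOVA for variables measured more than once. No covariate, stratum or subgroup is named.

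**The concern.** The protocol itself links FIBTEM to the amount of cryoprecipitate an infant may receive. A low value at rewarming makes a low value on the next ROTEM more likely, particularly in an infant given saline, and a low value is one of the triggers. Baseline FIBTEM is therefore plausibly prognostic for at least one component of a primary endpoint, and perhaps for bleeding.

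With 15 infants per arm, two things follow from leaving it out. Variation in the outcome that baseline FIBTEM could explain stays in the error term. And if one arm happens to contain more low-FIBTEM infants, its cryoprecipitate volume shifts without any drug effect, and the planned analysis has no means of correcting the estimate. What is at stake is precision and the credibility of one small trial's point estimate. The validity of the test is not in question.

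**Working it through.** **Inputs from the documents.** 15 infants per arm; significance at p ≤ 0.05, taken as two-sided; cryoprecipitate dose 10 cc/kg; FIBTEM cut points 15 mm and 7 mm. The sample size of 30 comes with no effect size, SD or power, so there is no planned figure to reproduce.

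**Assumptions, because the documents give no values.** Share f of infants below 7 mm at rewarming: 30%, 50% or 70%. Mean number of cryoprecipitate doses (Poisson): below 7 mm, 1.2 on placebo and 0.3 on RiaSTAP; at 7-15 mm, 0.1 in both arms.

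**1. Chance imbalance.** For two Bin(15, 0.5) counts, the difference plus 15 is Bin(30, 0.5). P(|difference| ≥ 3) = 1 − P(13 ≤ B ≤ 17) = 1 − (0.1445 + 2 × 0.1354 + 2 × 0.1115) = 0.36. Under the assumed placebo rates, an excess of 3 such infants moves an arm's mean by (3/15) × (1.2 − 0.1) × 10 = 2.2 cc/kg with no drug effect. The assumed true difference at f = 50% is 0.5 × (1.2 − 0.3) × 10 = 4.5 cc/kg.

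**2. Precision for cryoprecipitate at f = 50%.** Variances are in (cc/kg)².
- Placebo arm: within strata 100 × (0.5 × 1.2 + 0.5 × 0.1) = 65; between strata 0.25 × 11² = 30.25.
- RiaSTAP arm: within 100 × (0.5 × 0.3 + 0.5 × 0.1) = 20; between 0.25 × 2² = 1.
- Unadjusted SE = √[(65 + 30.25 + 20 + 1)/15] = 2.78; 4.5/2.78 = 1.62.
- With one stratum term, the common slope is (11 + 2)/2 = 6.5, leaving 0.25 × 4.5² = 5.06 between strata in each arm. SE ≈ √[(65 + 5.06 + 20 + 5.06)/15] = 2.52; 4.5/2.52 = 1.79.

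The SE falls by about 9%.

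**3. Power for cryoprecipitate by simulation, 15 v 15.**

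| Share below 7 mm | True difference (cc/kg) | Unadjusted t-test | One FIBTEM term |
|---|---|---|---|
| 30% | 2.7 | 14% | 18-19% |
| 50% | 4.5 | 31-32% | 37-39% |
| 70% | 6.3 | 53% | 59-60% |

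Ranges cover separate simulation runs. With no drug effect, both analyses reject in 4-5% of trials.

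**4. Bleeding.** Suppose the effect is 1 SD at 7-15 mm and zero below, and FIBTEM is not otherwise prognostic. Power at the three shares is then about 42%, 24% and 12% unadjusted and 44%, 25% and 11% adjusted: no useful gain. Suppose instead that half the infants are below 7 mm, low FIBTEM shifts bleeding by 1 SD, and the effects are 0.3 SD below 7 mm and 1.0 SD above. Adjustment then raises power from 29% to 38%. Without that shift it is 39% unadjusted and 38% adjusted.

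**5. Validity of the unadjusted test.** With a 1 SD prognostic shift and no drug effect, it rejects in 5.0% of trials. With effects of 0.3 and 1.0 SD in equal strata, the mean estimate is 0.65 SD, which is the population average.

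**6. What a stratum can show.** At f = 50% there are about 7.5 infants per arm in each stratum. The difference detectable with 80% power is (1.96 + 0.84) × √(2/7.5) = 1.45 SD (1.51 SD at 8 per arm and 1.63 SD at 7 by the t distribution). For the difference between strata it is 2.80 × √(4/7.5) = 2.05 SD.

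**The case against.** A reader might go further and infer that the trial mixes two comparisons: RiaSTAP against cryoprecipitate below 7 mm, and RiaSTAP against no fibrinogen at 7-15 mm. On that reading the pooled result could be attributed to neither. The doses make this tempting: at the Background's figure of about 15 g/L, 10 cc/kg of cryoprecipitate carries 10 × 15 = 150 mg/kg of fibrinogen, against 70 mg/kg of RiaSTAP. The documents do not support it.

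- Only one contrast is randomised: RiaSTAP v saline, each followed by the same algorithm. Its average difference is attributable to RiaSTAP and answers the stated goal. Cryoprecipitate is an outcome after randomisation, not an assigned comparator.
- Rewarming 7 mm does not divide the controls cleanly. The listed trigger also needs significant bleeding and is read on later ROTEMs. CFT is a second route. FFP, which the protocol names as a fibrinogen source, can be given in either arm, and RiaSTAP infants may receive cryoprecipitate too.
- Adjustment would not repair such a defect. The adjusted difference is still one average, and the stratum estimates are too imprecise to explain a null result.

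A further objection is that the test's error rate already allows for chance imbalance, and that the share below 7 mm and the dose rates are assumed. Both points are correct. They limit the size of the benefit and keep the severity low. They do not remove the case for using a baseline value that the trial collects anyway and that its own algorithm links to an endpoint.

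**Conclusion.** The point holds as a modest matter of precision and chance imbalance, at low severity. The planned comparison is unbiased and keeps its error rate. It leaves out a variable that is measured in every infant before study drug and is tied by the protocol to a primary endpoint. Under the assumed dose rates, adjustment adds about 4 to 8 percentage points of power for cryoprecipitate volume. For bleeding the gain runs from nothing to about 9 points, depending on how prognostic FIBTEM proves to be. The 36% imbalance figure assumes that half the infants are below 7 mm and that the arms are exactly 15 and 15.

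Separately, Drug protocol contains two statements that do not agree. One gives cryoprecipitate when the ROTEM shows fibrinogen deficiency and mentions no bleeding condition. The other gives no transfusion when the TEM is abnormal but bleeding is insignificant. The Figure 2 drawing is not in the text available here, so whether it settles the matter cannot be checked. The answer affects how strongly FIBTEM governs cryoprecipitate use.

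**What to change.** In Statistical Analyses:

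1. State the contrast as RiaSTAP v placebo, each on top of the shared transfusion algorithm.
2. Pre-specify that the group differences in 24-hour bleeding and in the volume of each transfused component are adjusted for rewarming FIBTEM MCF. Use one term, either below 7 v 7-15 mm or the continuous value, and fix the choice before unblinding.
3. Report the differences by FIBTEM stratum with 95% intervals as descriptive only. Do not claim that a stratum isolates a cryoprecipitate or a no-fibrinogen comparator, and do not split infants by whether they received cryoprecipitate.

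The two Drug protocol statements on cryoprecipitate must also be reconciled by those responsible for the clinical rules.

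The cost is a few lines of text and one degree of freedom. No new measurement or additional infants are needed, and the entry limit is unchanged. The downside is that the stratum estimates will be imprecise.
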